#### **Randomization and blinding procedures**

The randomization scheme will be generated and maintained by the Statistical and Data Coordinating Center (SDCC) at the Emmes Corporation, Rockville, MD. Participants will be randomized into the study cohorts manually using the assigned treatment code provided by Emmes. The assigned treatment information will be entered into the Emmes Corporation's AdvantageEDCSM electronic data capture system for each participant, after product administration has occured.

The pharmacist (or designee) with primary responsibility for dispensing study products is responsible for maintaining security of the treatment assignments.

#### **Analysis Population**

Definitions of analysis populations to be analyzed are:

#### **Enrolled Population**

All screened participants who provide informed consent, regardless of the participant's randomization and treatment status in the trial.

#### Full Analysis (FA) population

All participants in the enrolled population who are randomized, receive a study vaccination, and have pre- and/or post-vaccination immunogenicity measurement(s). This population will serve as the supportive population for the immunogenicity objectives.

#### Per Protocol Populations

The per protocol populations will be specified per sample and antigen type. All participants in the FA population who receive both doses of the same study vaccine and have post second dose (all sample types) and pre-vaccination (stool and plasma) immunogenicity measurement(s), with no major protocol or laboratory test SOP violations that are determined to potentially interfere with the immunogenicity assessment of the study vaccine, will be included in the per protocol populations. These populations will serve as the primary analysis populations for the immunogenicity objectives.

The specific criteria for exclusion of subjects from the Per Protocol Populations will be established before breaking the blind and will be based on the blinded review of protocol and laboratory test SOP violations

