# **Continued Eligibility Criteria**

Fulfilment of all of the following continuing eligibility criteria is required for all participants to receive their second vaccination (Day 14). If a participant does not meet the following continuing eligibility criteria prior to receiving their second immunization, vaccination can be deferred by up to two days. However, if a participant falls outside this deferred window, he/she will not receive the second vaccination but encouraged to continue all safety follow-up activities per protocol.

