# **Exclusion** Criteria

- 1. History of diarrhea during the 7 days before vaccination (see Protocol definition of diarrhea)
- 2. History of febrile illness within 48 hours prior to vaccination and fever at the time of immunization (fever is defined as a temperature ≥ 37.5°C (99.5°F) on axillary, oral, or tympanic measurement)
- 3. Current use of iron or zinc supplements within the past 7 days; current use of antacids (H2 blockers, omeprazole, OTC agents) or immunosuppressive drug
- 4. Receipt of antimicrobial drugs for any reason
- 5. Non-conformance to the protocol
- 6. Culture positive for ETEC, *Shigella*, *V. cholerae*, *Salmonella* or Rotavirus (the latter for all children <5 years of age) within 7 days of vaccination only if diarrhea was observed during post-dose 1 follow-up period
- 7. Acute disease at the time of vaccination visit or any time during the previous 3 days

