### Day 7 (to be defined by 7 ± 1 days after Day 0) – Clinic follow-up visit

On Day 7 ( $\pm$  1 calendar day if necessary for participant compliance), the participant will return to the study clinic and the following procedures occur:

- a) Any topics or new information considered by PI to be important to continued informed consent will be shared with the participant/parent/guardian.
- b) Interim medical review, concomitant medications review, and AE review will occur.
- c) A blood sample will be collected for hematology and clinical chemistry, as well as for immunology if sufficient blood is obtained (see Appendix I). Additional blood tests may be performed as necessary to follow-up and evaluate any abnormalities identified in monitoring labs.

- d) Vital signs will be measured
- e) A fecal sample will be collected for measurement of antibody responses.
- f) Study staff will instruct the participant or parent/guardian regarding continued assessment of his/her or the child's health and need to contact study staff (a) for follow-up of specific AEs, (b) if systemic symptoms worsen or do not resolve, and (c) if other AEs occur.
- g) The next visit for Day  $14 \pm 2$  days is scheduled.

Approximately 10 mL of blood will be collected from participants in Part A and 3.5 mL will be collected from participants in Parts B, C and D for the abovementioned assays at this visit.

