# Withdrawal from Further Vaccination and Early Termination from Study

An enrolled/vaccinated participant may be terminated from the study for any of these reasons.

- a) Participant or parent/guardian withdraws consent for any reason.
- b) PI, EMMES medical monitor, IPST, icddr,b DSMB or PATH medical monitor decides that termination is necessary to protect the participant, the integrity of the study, or achieve the objectives of the study.
- c) Interruption of study schedule makes the participant's data unusable according to protocol requirements.

Participants who are withdrawn from further vaccination will be encouraged to complete the safety-related participant follow-up. If the participant or parent agrees, other study procedures (e.g., blood sampling for measuring levels of antibodies) may be continued. Withdrawal from further vaccination may occur based on the local investigator decision at the time of an adverse event or based on the IPST review of these events on a cumulative basis if:

- (a) Participant experiences reactogenicity of Grade 3 or higher.
- (b) Participant experiences an event that contributes to study pause rules

In addition, participants may be withdrawn from further vaccination for any other safety-related reasons at the discretion of the PI, safety monitors, IPST, PATH medical officer, DSMB and the participant or the parent/guardian. The EMMES medical monitor and PATH medical officer will be informed of all issues related to withdrawal or termination of participant.

Participants or parents/guardians may withdraw themselves or their children, respectively, from study product administration due to what they perceive as an intolerable AE, or for any other reason. If withdrawal is requested, the participants or parents/guardians should be asked to have them or their child, respectively, continue (at least limited) scheduled evaluations, complete a study termination form, and be given appropriate care under medical supervision until the symptoms of any AE resolve or the condition becomes stable.

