#### Immunogenicity Analysis

For all immunological analyses, the response rate and magnitude of antigen-specific responses will be analyzed after each immunization as specimen availability allows; as well as the cumulative response rate after two immunizations (i.e. response after either immunization). Response rates to the five primary antigens in the ETVAX vaccine (LTB, CFA/I, CS3, CS5, and CS6) will be further evaluated to address co-secondary immunogenicity hypothesis by analyzing the response rates to at least two of the five different antigens by ALS IgA and fecal SIgA and to at least one of the five different antigens by plasma IgA. In addition, other analyses summarizing response rates to multiple antigens may also be performed. These multiple antigen response rate analyses will be based on the results from antigen-specific responses, including different age cohorts. For example, only antigens with statistically significant and/or clinically meaningful vaccine induced responses may be included in the analysis of multiple common antigen analyses.

For descriptive analysis of the magnitude of responses, levels of antibodies against CFA/I, CS3, CS5, CS6 and LTB in ALS and fecal extracts as well as plasma will be determined for each individual during screening and in all post vaccination samples. The geometric mean (GM) of antibody levels and the GM of fold-rises (post vaccination / pre-vaccination) will be determined for each study group and comparisons made between pre- and post-vaccination levels. The response rate for ALS IgA, fecal SIgA, serum IgA and serum IgG will be determined as the proportion of participants having a  $\geq$ 2-fold increase in antigen-specific antibody levels between pre- and post-vaccination samples. Additionally, other fold increases (e.g. 3-fold and 4-fold) will be explored. If insufficient amounts of pre-immune ALS specimens are obtained from young children and infants, to allow direct comparison between pre- and post immunization specimens, antibody levels in post vaccination specimens will be compared with the geometric mean ALS antibody level against corresponding antigen in the same age group.

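### The primary per-protocol sets require two doses and a post-dose-2 specimen even for the post-dose-1 (Day 7) response; defining them by time point as well would be a cheap improvement

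*Protocol*

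**What the plan says.** The section Per Protocol Populations sets the level of definition: "The per protocol populations will be specified per sample and antigen type". Membership covers "All participants in the FA population who receive both doses of the same study vaccine and have post second dose (all sample types) and pre-vaccination" measurements, the last for stool and plasma only, with no major protocol or laboratory violation. On their role: "These populations will serve as the primary analysis populations for the immunogenicity objectives". No exception is made for a particular visit. The Full Analysis population, which needs only a study vaccination and some immunogenicity measurement, is supportive.

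The section Immunogenicity Analysis states that "the response rate and magnitude of antigen-specific responses will be analyzed after each immunization as specimen availability allows", and adds a cumulative response rate over the two immunizations.

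At the Day 7 visit, "A fecal sample will be collected for measurement of antibody responses", and blood is taken for immunology if enough is obtained. Day 7 has a window of one day either side and dose 2 falls on Day 14 with two days either side, so this specimen always precedes dose 2.

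Several rules can stop dose 2. Under Continued Eligibility Criteria it may be deferred by up to two days for recent diarrhoea, fever, acute disease, antimicrobial use or a positive stool culture following diarrhoea. After that, "he/she will not receive the second vaccination but encouraged to continue all safety follow-up activities per protocol". Withdrawal from further vaccination may also follow if a "Participant experiences reactogenicity of Grade 3 or higher".

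**The concern.** The two-dose requirement suits an analysis of the response to two doses. Applied to the response to one dose, it makes membership depend on what happened after that response was measured. Some of those later events are illness or reactions. Diarrhoea and fever are both solicited reactions and grounds for withholding dose 2. The post-dose-1 response rate and geometric mean fold rise would then describe participants who took dose 1 and went on to complete the schedule, rather than all who took dose 1.

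At stake is the primary version of a secondary readout. It is conditioned on post-randomisation events whose frequency could differ between vaccine, vaccine plus dmLT and placebo. Some evaluable Day 7 results are also left out of groups that number only 10 to 30.

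**Working it through.** The protocol gives no figure for this loss, so there is none to reproduce. The check has two parts.

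**1. Reading the rules together.** Take a participant with a valid baseline and a valid Day 7 result.

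- Dose 2 is withheld under the continued eligibility criteria, or stopped after a Grade 3 reaction: the both-doses condition fails.
- Consent is withdrawn or the dose-2 window is missed: the same condition fails.
- Dose 2 is taken, but no later specimen is obtained: the post-second-dose condition fails. One route is vomiting within 30 minutes of dose 2. The Day 14 vaccination section then lists only the Day 42 and Day 182 safety follow-up, and Appendix I schedules no immunology specimen at either visit.
- The wrong product is given at dose 2: the same-vaccine condition fails. By contrast, the Safety Population section removes only data collected after mixed dosing starts and keeps the post-dose-1 data.

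In each case the participant leaves the primary Day 7 analysis although nothing about the Day 7 result has changed. The blinded review in Per Protocol Populations concerns protocol and laboratory violations; it does not lift the two-dose condition.

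**2. How large the effect could be.** Let m be the share of those with Day 7 results who are excluded, q the response rate in those retained, and k the ratio of the response rate in the excluded to q.

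Rate in all with Day 7 results = (1 − m)q + m·k·q.
Relative overstatement = m(1 − k) / [1 − m(1 − k)].

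There are two anchors for m, neither a measured rate for this trial:

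- Low: the Swedish adult trial OEV-121 (Table 2). Dose 1: 34 + 35 + 30 + 30 = 129. Dose 2: 34 + 34 + 30 + 28 = 126. Missed: 3/129 = 2.3%.
- High: the 10% drop-out allowance under Sample Size Calculation, a general allowance rather than a dose-2 withholding rate.

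The values of k are assumptions.

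| m | k = 0 | k = 0.5 | k = 1 | k = 1.5 |
|---|---|---|---|---|
| 2.3% | +2.4% | +1.2% | 0 | −1.1% |
| 10% | +11.1% | +5.3% | 0 | −4.8% |

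Example at m = 10%, k = 0: with 50% in those retained, the rate in all is 0.9 × 50% = 45%, and 50/45 − 1 = 11.1%. At k = 0.5 it is 45% + 0.1 × 25% = 47.5%, and 50/47.5 − 1 = 5.3%.

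These are single-arm figures. If m and k were the same in two arms, both rates would be multiplied by the same factor and their ratio would not change. A distorted ratio needs m or k to differ by arm.

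**Precision.** At 10%, 3 of 30 infants are excluded and the standard error of a mean log fold rise grows by √(30/27) = 1.054, about 5%. With a two-sample t-test, a 2-fold difference (log10 2 = 0.301), SD 0.6 and two-sided 5%, power is 44% with 27 per arm and 48% with 30. The 48% assumes that all three excluded infants have a usable Day 7 specimen. The protocol states about 73% for these inputs; that mismatch is a separate matter and does not bear on this point.

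**The case against.** The strongest case is that the affected analysis is peripheral and already covered. Safety is the primary objective. The immunogenicity hypothesis is judged in fully immunized children and infants, for whom a two-dose set is right, and it also suits the cumulative rate. The stand-alone post-dose-1 readout depends on specimen availability, all immunogenicity comparisons are called exploratory, and cohort progression is decided on safety data. One common set also allows dose-1 and dose-2 responses to be compared in the same people. Population flags are ordinary SAP content. All of this stands as a limit on severity. It does not remove the point, because the protocol itself states the rule and gives the primary role to the sets it defines, and the paired comparison can keep its own two-dose set.

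A reader might infer more than the documents support:

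- That valid Day 7 data are lost to the study. They are not; the Full Analysis set keeps them as supportive.
- That illness and reactions are the only cause. Withdrawal, a missed window or a missing later specimen act the same way, and withdrawal after a Grade 3 reaction is discretionary.
- That post-dose-1 rates are overstated by 11%. That needs 10% excluded and none of them responding, and no evidence in the protocol shows that the excluded respond less.
- That the comparison of arms is biased. Table 2 of the protocol reports no significant difference in solicited events between arms in OEV-121. Those were Swedish adults, so this does not settle the matter for children, but differential exclusion here remains conjecture.

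**Conclusion.** The point holds, at minor severity, as a cheap improvement. As written, the primary per-protocol rule for the post-dose-1 analysis depends on later events that have no bearing on whether the Day 7 result is valid. It conditions a secondary, exploratory readout on post-randomisation events and costs a little precision.

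The size and direction of any bias cannot be derived from the protocol. Over an assumed 2% to 10% excluded, it runs from none, if the excluded respond equally, to about 11% relative overstatement, if 10% are excluded and none respond; it turns negative if they respond more often. Near the exclusion seen in the Swedish adult trial, it is at most about 2.4% upward. The safety analyses, the two-dose analyses and the immunogenicity hypothesis in fully immunized children are unaffected.

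**What to change.** In Per Protocol Populations, define the sets by sample type, antigen and time point. For post-dose-1 (Day 7) analyses, require dose 1 as assigned, the pre-vaccination specimen where applicable, an evaluable Day 7 specimen and no major deviation up to Day 7. Do not require dose 2 or a post-dose-2 specimen. Keep the present two-dose definition for post-dose-2, cumulative and paired dose-1 versus dose-2 analyses.

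The cost is a short wording change in the protocol or SAP and one time-point flag, settled before unblinding. No participants, specimens or visits are added, and dosing and eligibility rules stay as they are. The small downside is that denominators will differ between the Day 7 and post-dose-2 tables, which a footnote can explain.

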# The Safety Population

All participants in the enrolled population who receive a study vaccination and have safety data available. Treatment groups for safety analysis will be assigned according to the actual treatment received at Day 0. If a participant receives mixed doses (e.g. an ETVAX dose without dmLT at Dose 1 and the same ETVAX at Doses 2 with dmLT), the safety data collected after the start of the mixed dosing (e.g. post Dose 2) will be excluded from the analysis. All excluded data will be presented in the data listings. All safety analyses will be performed using this population.

Any additional exclusion from the Full Analysis population if warranted (e.g. a significant protocol deviation that is determined to potentially interfere with the vaccine induced immune responses) based on the blinded review of the data will be established and documented before breaking the blind.

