# **Primary Endpoints**

Safety and tolerability:

- Number of SAEs
- Number of AEs
- Number of vaccine induced reactogenicity events

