#### **Safety Analysis**

The incidence of any adverse events (AEs) will be determined. Gastrointestinal and systemic AEs will be assessed postvaccination using participant/parent/guardian interview (including memory aids), targeted physical examinations, vital signs and clinical laboratory tests and reactogenicity assessments to be completed following each vaccination. The solicited AEs of nausea (Part A only), abdominal pain/stomach ache (Parts A and B only), fever, vomiting and diarrhea will be evaluated daily by the TSS for 7 days post vaccination. Unsolicited AEs will be assessed through Day 42 and serious adverse events (SAEs) will be assessed over the entire duration of the study. Proportions of subjects with events, overall, by grade and relationship with vaccination will be analyzed for each of the vaccine arms in comparison to the placebo arm. For the analysis of the solicited adverse events, the statistical comparisons using Fisher's exact test will be performed using two-sided 5% Type I error rate without an adjustment for multiple comparisons. The primary purpose of statistical comparisons are to screen potential AEs that need further clinical evaluation. Therefore they are not considered formal statistical hypothesis testing and it is acknowledged that there will be an inflated Type I error rate (i.e. inflated false statistical significances) due to performing multiple testing without an adjustment.

Safety will be assessed by analyses of the following primary endpoints (events), where the unit of analysis in each case will be the proportion of participants with at least one event:

- Solicited gastrointestinal reactions
- Solicited systemic reactions
- Unsolicited adverse events
- Adverse events where there is a reasonable possibility that the study product caused the event, i.e., are suspected adverse reactions
- Serious adverse events

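### The Safety Population rule drops all safety data after a mixed-dosing error, SAEs included, from every safety analysis, although these events are the primary endpoints.

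*Protocol*

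**What the plan says.** The protocol's Safety Population section includes everyone who was vaccinated and has safety data. It sets the groups thus: "Treatment groups for safety analysis will be assigned according to the actual treatment received at Day 0". It then deals with participants whose two doses differ, giving as its example "an ETVAX dose without dmLT at Dose 1 and the same ETVAX at Doses 2 with dmLT". For them, "the safety data collected after the start of the mixed dosing (e.g. post Dose 2) will be excluded from the analysis". Two further sentences fix the reach of the rule: "All excluded data will be presented in the data listings" and "All safety analyses will be performed using this population".

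The Primary Endpoints section lists "Number of SAEs", together with the numbers of AEs and of vaccine-induced reactogenicity events. The Safety Analysis section says: "Unsolicited AEs will be assessed through Day 42 and serious adverse events (SAEs) will be assessed over the entire duration of the study". It names five classes of event, SAEs among them, and for these "the unit of analysis in each case will be the proportion of participants with at least one event".

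**The concern.** Safety is the primary objective, and the excluding sentence covers safety data without qualification. An SAE, a death or a Grade 3 reaction after a wrong second dose would be collected and reported, then left out of the tables that answer the primary question. The exclusion depends on something that happens after exposure to study product, and it removes what follows that exposure. No other section returns the events to the by-group analysis through an as-treated group, an any-exposure summary or a sensitivity analysis.

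The listings are an incomplete safeguard. The Interim Analysis section allows an unblinded analysis of each Part once follow-up to Day 42 is complete, to inform decisions such as preparing another study, and states that it will contain no individual listings. If the Safety Population rule is applied there, a dropped SAE would be in neither a table nor a listing of that report.

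Dose groups have 15 participants in Parts A to C and 30 in Part D. At that size one event separates a result of none observed from a possible signal.

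**Working it through.** **1. The protocol's own figures (Sample Size Calculation).**

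Chance of at least one event: 1 − (1 − p)^n.
- n = 15: 80.4% at p = 10.3% and 90.1% at 14.3%. The protocol states about 80% and 90%.
- n = 30: 80.5% at 5.3% and 90.0% at 7.4%. The protocol again states about 80% and 90%.

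Exact one-sided 95% upper bound with zero events: 1 − 0.05^(1/n).
- n = 15: 18.1% (stated: about 18%).
- n = 30: 9.5% (stated: about 9.5%).

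All of these reproduce.

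**2. Follow-up removed by an error at Dose 2.** Nominal days: Dose 2 on Day 14, end of unsolicited-AE collection on Day 42, final visit on Day 182.
- SAEs: (182 − 14)/182 = 168/182 = 92%.
- Unsolicited AEs: (42 − 14)/42 = 28/42 = 67%.
- Solicited reactions: one of two 7-day windows, 1/2 = 50%.

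**3. Effect of one dropped SAE.** Assumption: one mixed-dosed participant in a group has an SAE after Dose 2 and would otherwise be counted in the Day 0 group. With one event, the exact upper bound is the p that solves (1 − p)^n + n·p·(1 − p)^(n−1) = 0.05.

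| Group size | Event kept | Upper bound | Event dropped | Upper bound |
|---|---|---|---|---|
| 15 | 1/15 = 6.7% | 27.9% | 0/15 | 18.1% |
| 30 | 1/30 = 3.3% | 14.9% | 0/30 | 9.5% |

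The dropped-event bounds are the figures that the protocol quotes for a group in which no SAE is observed.

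If the participant were also taken out of the denominator, the result at n = 15 would be 0/14, with upper bound 1 − 0.05^(1/14) = 19.3%. The SAE is missing either way.

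**4. Effect on detection.** The protocol gives no frequency of mixed dosing. Assume m = 1, 2 or 3 affected participants in a group, none contributing data after Dose 2. The chance of seeing at least one event in that period is then 1 − (1 − p)^(n−m).
- n = 15, p = 14.3%: 90.1% falls to 88.5%, 86.6% or 84.3%.
- n = 30, p = 7.4%: 90.0% falls to 89.2%, 88.4% or 87.5%.

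The average loss is small. What matters is the single event in step 3.

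**The case against.** **The events are not lost.** Excluded data stay in listings. SAEs go to the DSMB and ERC within 24 hours, the IPST receives ongoing SAE listings, and the pause rules act on participants rather than on an analysis population. All of this stands, and a reader who infers that the rule hides SAEs from safety oversight would be wrong. The protocol also promises to summarise the Day 182 information in the final report, with no exception for mixed dosing. That visit covers only what is new since the previous one, and the promise does not put the events back into the comparison by group.

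**Errors should be rare.** A second unblinded person checks preparation. By the allocation tables, only Part A runs vaccine alone and vaccine plus dmLT in the same cohort, although a placebo and vaccine mix-up is possible in any Part. This limits the expected effect, but it does not justify the rule.

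**The denominator is not stated.** The protocol sets no denominators table by table, and the SAP may do so. Hence the condition attached to the incidence statement in the verdict. The exclusion itself is fixed in the protocol.

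**The 1/15 figure depends on attribution.** This is correct. In the protocol's own example, attributing the event to the product received at Dose 2 puts it in the vaccine plus dmLT group. There it would be 1/16, with an upper bound of about 26.4%, rather than 1/15 in the Day 0 group.

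**Conclusion.** The point holds. A rule stated in the protocol can remove a real SAE or severe reaction from the primary safety tables, against the protocol's own endpoints and follow-up plan. For each participant with an error at Dose 2, it discards 92% of SAE follow-up, 67% of unsolicited-AE follow-up and half of the reactogenicity observation. If the participant stays in the Day 0 group's denominator, that group's reported incidence can only fall or stay the same. The illustration in step 3 rests on one affected participant having an SAE, and no document gives the chance of that.

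Three stronger readings are not supported:

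- A reader might infer that the rule always makes the vaccine look safer than placebo. An error can also reduce exposure (vaccine then placebo, or vaccine plus dmLT then vaccine alone), and events dropped from the placebo group would make the vaccine look relatively worse. The direction of any between-group bias depends on the arm in which the error occurs.
- A reader might infer that an SAE would be lost from a Fisher comparison. The Safety Analysis section specifies Fisher's exact test for solicited events only, and as a screen rather than a formal test.
- A reader might apply the 92% to all safety data. It applies only to SAE follow-up.

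**What to change.** Delete the exclusion from the Safety Population section and keep all post-vaccination safety data in the safety analysis. Attribute each event to the product actually received at the most recent preceding dose, so that Dose 1 events stay with the Dose 1 product. Counting such participants throughout under their highest exposure would be worse, because a Dose 1 event would then be credited to a product not yet taken.

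Footnote mixed-dosed participants in the any-dose and SAE tables, naming both products received, so that a late event after two different products is not read as belonging to one alone. Keep the current exclusion only as a sensitivity analysis.

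The cost is a reworded sentence in the population definition and a table footnote. The small downside is that a few participants contribute to two product groups in the per-dose tables.
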